The study was a cross-over pilot clinical study consisting of two periods. The first period was only an observational and monitoring phase where participants just continued with their regular diet (RD), for this reason all participants initiated this period and wash-out term was no needed. Subsequently, with the data of the first phase obtained, the subjects began the second period in which they had to undergo a nutritional intervention with a quinoa diet (QD).

[figure not shown]
A total of six visits plus two quinoa products collection days were programmed (**Figure 1**). After the pre-study visit (V0) which took place a week before start nutritional intervention and where researchers obtained signed informed consent, participants were summoned for a first visit (V1) where they were explained how they should fill in the dietary records and they were applied with the FreeStyle Libre®.

Subjects then began RD, a period of 4 weeks during which only their normal life was monitored. After the first 14 days of this, a second visit (V2) was made where the dietary record was collected that would serve to account for their usual consumption of cereals, flours, tubers and legumes, the FreeStyle Libre® sensor was also collected.

The last day on RD period, on day 28, they were cited (V3) in consultation where blood samples after an 8 hours fast, anthropometrics measurements and blood pressure measure where obtained and for the placement of the new FreeStyle Libre® sensor. Participants were asked about their physical activity and exercise practice during those past 4 weeks by a short questionnaire adapted from the Minnesota Leisure Time Physical Activity Questionnaire for individuals of advanced age (VREM questionnaire) and a new empty 14-day dietary record was given. In addition, the volunteers received the first foods with quinoa to initiate QD the next day. Products were delivered weekly, for conservation reasons but also to ensure that they followed an adequate consumption, they had to go through consultation to pick up the product and gave the researchers the empty packs where quinoa products had been.

On the next visit the day 42 (V4) the Freestyle Libre® sensor was collected and the filled dietary record was collected. Finally, after 28 days of quinoa diet they were summoned for the last visit the day 56 (V5) where all the determinations were repeated identically as V3.

Figure 1. Study design and visits

Study food

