With the premise that the products created replaced not only grains, legumes or tubers, but also farinaceous commonly consumed by the participants and that only the cereal fraction was modified, similar products based on quinoa flour were created. The creation of these products was necessary, after conducting a market search where it was observed that there was not enough food to replace those consumed since these had percentages of quinoa flour not exceeding 20-30%.

Thus, apart from delivering quinoa, quinoa flakes and quinoa flour to the participants, they were given products created with $\geq 70\%$ quinoa flour and were biscuits, crackers, brioche, sponge cake, baguette bread, sliced bread and pasta (**Table 1**). Moreover, a quinoa-based recipe was delivered with eight commonly consumed recipes that replaced the tuber, legume or grain of the recipe. Each subject received the equivalent of what they

consumed according to their RD dietary records. Thus, only if the volunteer had indicated that he consumed sponge cake was the quinoa-based product delivered to him.

Table 1. Comparison of nutritional values of products marketed in a regular diet with similar ingredients than products based on quinoa for the study.

[figure not shown]
Statistical analyses

Calculations and Statistical Analyses

Descriptive data are presented as the mean and standard deviation (SD) or median and interquartile range (IQR) for continuous variables, and the frequencies and percentages (%) for categorical variables. Anthropometric measurements, blood test variables and dietary intake were compared at different times using the non-parametric Wilcoxon signed rank test because normality and equality of variance could not be assumed due to small sample size (n=9). In order to compare variables related to dietary patterns, mean value for dietary intake, including all meals, was considered for each participant.

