The glucose level monitoring sensor takes measurements at discrete time points for each patient (**Figure 2 A**). Therefore, firstly the glucose curves have been linearly interpolated in order to have observations for each patient at equal time points (**Figure 2 B**). A first sight to the glucose curves over the day shown that they were more homogeneous around breakfast than around other later meals intakes. Therefore, the glucose concentration values corresponding to the breakfast were considered as a function of time in minutes over the interval $t = [-30, 120]$, that begins half an hour before the start of breakfast and ends two hours later. Before constructing a functional model, the functional data were time aligned in order to reduce the differences between different patients and/or different days (for instance, some patients could mark the starting time of breakfast systematically before than others, or spend systematically more time in breakfast than the average) (**Figure 2 C**). The time alignment has been done by warping functions, using the function WFDA in the R package fdapace.

Figure 2. Glucose concentrations of patients (A) at discrete time points (B) at equal time points with interpolation (C) as aligned curves

Once the glucose level curves have been synchronized, a functional regression analysis was conducted to model the effect of diet type, patient and nutrient intake on monitored glucose levels. Three different explanatory variables have been considered: diet type with two categories (regular and Quinoa diets), patient indicator (categorical variable with nine levels) and the contents in different nutrients. The breakfast glucose curves are handled as the functional response variable. To study the relationship between these variables function on scalar regression (fosr) models were used.

Firstly, the univariate effect of the diet type on glucose curves have been analyzed and then more complex fosr models with two factors (diet and patient factors) and scalar variables (nutrients) have been constructed. The most complex model including all effects of the independent variables is defined by the equation

$$g_{ij}(t) = \beta_0(t) + I_R^j \beta_R(t) + I_Q^j \beta_Q(t) + \alpha_i(t) + \sum_{k=1}^K x_k^{ij} \beta_k(t) + \varepsilon_{ij}(t),$$

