where i indicates the patient ($i = 1, \dots, 9$), j indicates the day of observation ($j = 1, \dots, 28$), $g_{ij}(t)$ is the glucose curve observed the day j for patient i , I_R^j takes value 1 for regular diet and 0 for Quinoa diet, $I_Q^j = 1 - I_R^j$ is the indicator of Quinoa diet, x_k^{ij} is the content of nutrient k in the breakfast that patient i takes in the day j ($k = 1, \dots, K$) and $\varepsilon_{ij}(t)$ is a random noise function with expected value 0 for all t and independent from noise function corresponding to other days or patients. According to this model, the overall shape of glucose curves is described by the functional coefficient $\beta_0(t)$, the diet effect is summarized by the functions $\beta_R(t)$ and $\beta_Q(t)$ (by construction, they verify that $\beta_R(t) = -\beta_Q(t)$), functions $\alpha_i(t)$ measure the individual effects (by construction, $\sum_{i=1}^9 \alpha_i(t) = 0$) and $\beta_k(t)$ function shows the effect of every nutrient k . The functional

regression models have been fitted by penalized flexible functional regression, as implemented in the function pffr of the R package refund.

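### The glucose-curve model has a patient effect but no patient-by-diet term, so any diet band or p-value from it counts up to 252 curves when only 9 participant differences inform the diet contrast

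*Combined protocol and SAP*

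**What the plan says.** Under the heading Calculations and Statistical Analyses, breakfast glucose curves are the response in function-on-scalar regressions fitted with pffr. First "the univariate effect of the diet type on glucose curves have been analyzed". Larger models then add the "patient indicator (categorical variable with nine levels") and breakfast nutrient contents. The fullest model has an overall curve, a diet effect, a patient curve α_i(t), nutrient terms and noise. α_i(t) has no diet index, so it is the same under both diets. The noise is stated to be "independent from noise function corresponding to other days or patients". Days are indexed 1 to 28. The documents name no random block term, cluster-robust variance, participant-level resampling, significance level, band or standard-error method for these models.

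The Study design section fixes how the curves arise. The first sensor is worn at the start of the regular-diet period: "After the first 14 days of this, a second visit (V2) was made", and the sensor was collected then. Visit V3, on day 28, was among other things "for the placement of the new FreeStyle" sensor, which was collected on day 42 during the quinoa period. The order was the same for everyone: "all participants initiated this period and wash-out term was no needed".

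Elsewhere the plan works at participant level. For dietary patterns the "mean value for dietary intake, including all meals, was considered for each participant", and anthropometric, blood and dietary variables are compared by Wilcoxon signed rank tests on n = 9.

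**The concern.** Diet changes once per participant, at the same moment as the sensor and the calendar period. Three things can move all of one participant's curves in a block together: that person's own response to quinoa, a difference between the two sensors, and drift between the periods. A patient curve common to both diets cannot absorb a shift that differs between a person's two blocks, and no other term is provided for it. The residuals within a block are then correlated, contrary to the stated assumption, and the model treats repeated days as independent evidence on diet.

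This is the only analysis described for the sensor curves. If bands or p-values for diet are read from it, chance differences between nine pairs of blocks can be presented as an effect of quinoa.

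**Working it through.** The plan states no power, significance level or interval that could be reproduced. Only the index ranges can be checked, and they agree: 14 + 14 sensor days = 28, and 9 × 28 = 252 curves at most (missed scans or unrecorded breakfasts reduce this).

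**Inputs from the documents:** 9 participants; 2 blocks each; n = 14 days per block, inferred from the visit days and the day index.

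**Assumed inputs:** day-to-day SD s and participant-by-block SD τ, since the documents give neither. The calculation is for balanced data at one time point, without penalisation.

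**Degrees of freedom**
- Patient + diet model: 252 − 9 − 1 = 242; two-sided 5% cut-off 1.970.
- Nine paired differences: 9 − 1 = 8; cut-off 2.306.

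**Standard error.** Let θ = τ²/s².
- True variance of the diet difference: (2s²/126)(1 + 14θ).
- Variance the model expects: (2s²/126)[234 + 8(1 + 14θ)]/242 = (2s²/126)[1 + (112/242)θ].
- Squared true/model SE ratio: (1 + 14θ)/(1 + (112/242)θ). This exceeds 1 for every θ > 0, so the direction does not depend on the assumed SDs.

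Example, s = 15 and τ = 4: θ = 16/225 = 0.0711; ratio² = 1.9956/1.0329 = 1.932; ratio = 1.39.

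**False rejection.** With v = s² + nτ², the diet mean square is v·χ²(1), and the residual sum of squares is v·χ²(8) + s²·χ²(18(n − 1)). Simulating these components for a nominal 5% test with no diet effect gives:

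| Block SD τ (mg/dL) | SE ratio, s = 15 | Rejects, s = 15 | Rejects, s = 10 | Rejects, s = 20 | Rejects, s = 15, n = 10 |
|---|---|---|---|---|---|
| 0 | 1.00 | 5.0% | 5.0% | 5.0% | – |
| 2 | 1.11 | 7.8% | 11.3% | 6.6% | 7.0% |
| 4 | 1.39 | 15.8% | 25.8% | 11.3% | 12.7% |
| 6 | 1.74 | 25.8% | 38.8% | 18.2% | 20.6% |
| 8 | 2.10 | 35.0% | 47.9% | 25.8% | 28.5% |

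The last column is for 10 usable breakfasts per block: 180 − 9 − 1 = 170 residual df. The paired participant-level t-test rejects 5.0% throughout.

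**Nutrient terms.** In 2,000 simulated trials with smooth curves on 11 grid points and s = 15, the model with patient and four nutrient terms unrelated to the block shift (242 − 4 = 238 df) rejected 4.8%, 13.6% and 30.1% for τ = 0, 4 and 8. A sign-flip test using the maximum statistic over time rejected 5.3%, 4.9% and 4.3%.

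**Diet-only model.** It ignores the pairing, so between-patient variance enters its residual. The expected residual variance is [234s² + 8v + 8(v + 28σ_p²)]/250. Take s = 15 and patient SD σ_p = 10.
- τ = 0: v = 225; residual = (52,650 + 1,800 + 24,200)/250 = 314.6; SE ratio = √(225/314.6) = 0.85.
- τ = 8: v = 225 + 14 × 64 = 1,121; residual = (52,650 + 8,968 + 31,368)/250 = 371.9; SE ratio = √(1,121/371.9) = 1.74.

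This model can therefore err in either direction.

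**The case against.** The strongest reply is that the plan promises no inference: it describes a pilot, sets no significance level and summarises the diet effect by coefficient functions. In the balanced case without nutrients, the missing term leaves the estimated diet curve unchanged and affects only its uncertainty. That is right, and the point is conditional for that reason.

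The variances are assumed, and the rates come from unpenalised calculations, not from a pffr fit. Smoothing, within-curve correlation and time alignment are not reproduced in the one-time-point calculation. That also stands: the direction is established, but the size is illustrative. A block SD of exactly zero would require nine identical responses to quinoa, interchangeable sensors and no individual drift.

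Nutrient terms could absorb part of a shift that arises from intake. They could not absorb a sensor offset.

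If inference is restricted to these nine people, differing responses to quinoa are part of their average effect and not error. That narrows the point, but sensor and period offsets remain unmodelled under that reading too.

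The fixed order may well be a larger problem. It is a separate bias, and neither the present model nor the remedy removes it.

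**Conclusion.** The concern holds. The stated independence does not match a design in which diet, sensor and period change together once per participant. For models with a patient effect, the standard error for diet is too small whenever a participant-by-block component exists; with none, the model is valid. At day SD 15 mg/dL and block SD 2 to 8 mg/dL, the true SE is 1.11 to 2.10 times the model's, and false rejection is about 8% to 35%. Over day SDs of 10 to 20 and block SDs of 0 to 8, the range is 5% to 48%. These figures rest on assumed variances, balance and a single time point. The diet-only model is not uniformly too optimistic, but it too is unsuitable for inference because it ignores the pairing. The model needs correcting before any claim about diet is drawn from the curves.

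**What to change.** - Keep the pffr model with patient and nutrient terms, and add a functional random intercept for each patient-by-diet block (9 × 2 = 18 levels). The term must be random: a fixed interaction tested against day-level noise would leave the problem in place.
- Refer the diet effect to 8 df. At s = 15 and τ = 2, 4, 6 and 8, a 1.96 cut-off with this term still rejects 5.4%, 7.4%, 8.3% and 8.5%. On 8 df the rates are 2.5%, 4.0%, 4.7% and 5.0%, which is conservative when block variance is small.
- As the check on the unadjusted diet effect, average each participant's curves within diet and apply a sign-flip test to the 9 paired difference curves, using the maximum statistic over time. There are 2⁹ = 512 patterns, so the smallest two-sided p is 2/512 = 0.004. This check does not adjust for nutrients.
- Report the diet-only model as descriptive, and draw any diet inference from the two analyses above.
- State that these changes correct precision only. Everyone had the regular diet first, so diet stays confounded with period.

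The cost is SAP wording and re-analysis of existing data, with wider pointwise intervals. The widening is the SE ratio times 2.306/1.970 = 1.17: with s = 15, about 1.3, 1.6, 2.0 and 2.5 times for τ = 2, 4, 6 and 8, and 1.17 times if there is no block variance.
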